7.1.2.2 Treatment

The following assessments should be performed on the **first day of each cycle** (every 4 weeks) prior to receiving study treatment (+/- 7 days):

- The inclusion and exclusion criteria should be checked to ensure appropriate patients are treated at Day 1 of Cycle 1 only.
- Physical examination including vital signs (pulse and blood pressure), weight, temperature and examination of pertinent organ systems ECOG performance status

Phase II Study of Perindopril and Regorafenib in mCRC (PARICCA)

- Toxicity and adverse events documentation (including Start/Stop dates, seriousness, CTC notation and grading, relationship to study drug, outcome and action taken) using CTCAE v4.03
- Concomitant medications (including start/stop dates, dose, indication)
- Echocardiogram or MUGA scan only if clinically indicated. Echocardiograms or MUGA scans should be performed by the same operator to minimize inter-observer variability.

The following laboratory evaluations are not required at Day 1 of Cycle 1 if these were completed within 7 days of starting study drug treatment. Otherwise, these laboratory evaluations are required on Day 1 of each cycle:

- CBC with differential should be performed: RBC, hemoglobin, hematocrit, platelet count and WBC. WBC must include differential neutrophil, lymphocyte, monocyte, basophil and eosinophil counts. (note: BCCA lab does 5 part differentials).
- Electrolyte panel: sodium, potassium, chloride and Chemistry panel: Aspartate Amino-Transferase (AST), bilirubin (total and direct), alkaline phosphatase, triglyceride levels, uric acid, total protein, albumin, calcium, lipase, amylase, phosphate, Lactic Dehydrogenase (LDH), glucose, creatinine and Blood Urea Nitrogen (BUN)
- Thyroid function test (TSH, free T3, free T4)
- Coagulation panel: Prothrombin time (PT) or the International Ratio of PT (PT-INR) and Partial Thromboplastin Time (PTT). If a patient is on warfarin with stable PT/INR at baseline, the PT/INR should be assessed on Day 5 of Cycle 1. If either of these values is above the acceptable range, the doses should be modified and the assessments should be repeated weekly until it is stable.
- Urinalysis: appearance, pH, glucose, ketones, erythrocytes, leukocyte esterase, nitrite, bilirubin, urobilinogen, protein, creatinine, and protein/creatinine ratio. A microscopic analysis should be performed if the appearance is turbid, or if protein, leukocytes, erythrocytes or nitrite are out of normal range.
- Quantification of proteinuria by urinary protein/creatinine ratio on a random urine sample preferably taken at mid-morning. This should be reported as the ratio of concentrations of total urine protein (in mg/dl) to urine creatinine (in g/dl).
- Measurement of GFR according to the MDRD (Modified diet in renal disease) abbreviated formula.

The following items are not required at Day 1 of Cycle 1 if these were completed within 7 days of starting study drug treatment. Otherwise, these items are to be complete on Day 1 of each cycle:

- 12-lead ECG
- Assessment of AEs
- Concomitant medications
- Provide blood pressure diary to the patient

Phase II Study of Perindopril and Regorafenib in mCRC (PARICCA)

- Provide rash diary to the patient
- Provide patient education brochure to patient

The blood pressure must be monitored weekly for the first six weeks of study treatment. Either the blood pressure can be recorded by the treating physician and entered onto the CRF or by the patient and entered onto a patient diary. In the latter case, the patient should be instructed to contact the physician in the event of systolic ≥ 150 mm Hg and / or diastolic ≥ 100 mm Hg. The physician should confirm the reading before recording it into the CRF. Blood pressure measurements will be performed in patients sitting for 5 minutes prior to the evaluation. The patient should be instructed to take their blood pressure in the morning and repeat two more times for accuracy.

- Dispense study drug and perform drug accountability after Cycle 1.
- Photos will be taken of hands and feet for illustrative purposes.

The following assessments should be performed on **day 7 of the first cycle** (+/- 3 days):

- Physician visit
- ECOG Status
- Liver functions tests
- Blood pressure
- Assessment of AEs
- Concomitant medications
- Patient will have photos taken of hands and feet

The following assessments should be performed on **day 14 of the first cycle** (+/- 3 days):

- Physician visit
- ECOG Status
- Liver functions tests
- Blood pressure
- Assessment of AEs
- Concomitant medications
- Patient will have photos taken of hands and feet

The following assessments should be performed on **day 21 of the first cycle** (+/- 3 days):

- Physician visit
- ECOG status
- Liver Function Tests
- Blood pressure
- Assessment of AEs
- Concomitant medications

Phase II Study of Perindopril and Regorafenib in mCRC (PARICCA)

- Patient will have photos taken of hands and feet

The following assessments should be performed on **day 7 of the second cycle** (+/- 3 days):

- Blood pressure
- Assessment of AEs
- Concomitant medications

The following assessments should be performed on **day 14 of the second cycle** (+/- 3 days):

- Physician visit
- ECOG status
- Liver function tests
- Assessment of AEs
- Concomitant medications
- Blood pressure

Tumor measurements (CT/MRI scans) will be conducted every 8 weeks. A PET scan is not acceptable for radiological evaluation. Throughout the study, the identical lesions to those identified and measured at baseline must be evaluated using the same technique, and preferably by the same investigator/radiologist. MRI/CT scans must meet the standard of care for the imaging of lesions in the respective organ system(s). Copies of all imaging (CT scans, MRI, X-rays, ultrasound, photographs of cutaneous lesions, etc.) performed for tumor assessment in all enrolled patients will be stored electronically at the site.

7.1.2.3 End of Treatment Visit

When a patient is taken off treatment, the following assessments should be performed within 14 days (+/- 7 days) after study treatment has stopped:

- Brief medical history and complete physical examination including review of all organ systems, examination of pertinent organ systems, vital signs (heart rate, blood pressure and temperature) and weight
- ECOG performance status
- A CBC with differential should be performed: RBC, hemoglobin, hematocrit, platelet count and WBC. WBC must include differential neutrophil, lymphocyte, monocyte, basophil and eosinophil counts.
- Liver function tests
- CEA testing
- Creatinine
- Urinalysis: appearance, pH, glucose, ketones, erythrocytes, leukocyte esterase, nitrite, bilirubin, urobilinogen, protein, creatinine, and protein/creatinine ratio. A microscopic analysis should be performed if the appearance is turbid, or if protein, leukocytes, erythrocytes or nitrite are out of normal range.

Phase II Study of Perindopril and Regorafenib in mCRC (PARICCA)

- Quantification of proteinuria by urinary protein/creatinine ratio on a random urine sample preferably taken at mid-morning. This should be reported as the ratio of concentrations of total urine protein (in mg/dl) to urine creatinine (in g/dl).
- Measurement of GFR according to the MDRD (Modified diet in renal disease) abbreviated formula.
- 12-lead ECG
- Concomitant medications
- Toxicity and adverse events documentation
- For patients who discontinue for reasons other than disease progression, tumor measurements and evaluation of tumor response of all measurable lesions should be performed according to RECIST criteria, version 1.1.

7.1.2.4 Safety Follow-Up Visit

Patients have to be evaluated for symptoms and adverse events in a visit **30 days (+/- 7 days)** after permanently stopping study treatment. All AEs starting within 30 days after the last dose of study medication should be recorded. This contact may be completed via telephone. The following assessments should be performed:

- Concomitant medications (including anti-cancer medication)
- Toxicity and adverse events documentation

7.1.2.5 Follow-up Period

Physician visits: during follow up period, patients will be seen by physician every four weeks until disease progression, then every two months as per standard of care.

Patients removed from study for unacceptable adverse events will be followed until resolution or stabilization of the adverse event. After the 30-day follow up period, no additional AE will be reported.

- After the last contact of the Safety Follow-Up Visit (or after the EOT visit if the Safety Follow-Up Visit is not available), subjects will be off study.
- Status of disease and date of progression (If tumor assessments are available for subjects who have not yet experienced PD, enter the follow-up tumor evaluations in the CRF until PD is diagnosed).
- Date and cause of death while on study will be captured.
- Documentation of all new cancer therapies.

Telephone follow-up is acceptable. Site staff must use caution when contacting the subject's family for this information, especially if they are no longer under the care of the investigator, so as to not inadvertently cause any distress to the family of a subject who is no longer alive.

Subjects who withdraw consent from study drug treatment should enter the Follow-up Period (unless consent to follow-up is specifically withdrawn).

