Details for the premature termination of the study are provided in Section 10 (Premature termination of the study).

For all subjects who discontinue study treatment, relevant visit data will be entered into the case report form and any unused study drug will be accounted for and returned. Adverse events or clinical laboratory abnormalities that cause a patient to discontinue from study treatment should be followed until they recover or stabilized.

All subjects will enter the follow-up period upon discontinuation of the treatment drugs. Regardless of the reason for discontinuation all subjects will be followed for survival until death is documented, except for those who specifically withdraw consent to follow-up. Subjects who withdraw consent from study drug treatment may enter the Follow-up Period.

Assessment of survival status will be performed approximately every month. In addition, for subjects, who discontinue study treatment and have not experienced PD, available tumor assessments will be recorded in the CRF until PD is documented.

Phase II Study of Perindopril and Regorafenib in mCRC (PARICCA)

Death due to mCRC is not a serious adverse event. If any patient should die during the study treatment or within 30 days of their last dose of study drug, of causes NOT related to the disease itself (mCRC), the Investigator or a designated associate(s) will inform the Bayer HealthCare Medical hotline. If the cause of death is not related to the disease itself (mCRC), the cause of death should be recorded in detail within 24 hours of notification to the investigator on a Serious Adverse Event Form and transmitted to Health Canada.

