7.3 Efficacy

Phase II Study of Perindopril and Regorafenib in mCRC (PARICCA)

The primary endpoint of this trial is a safety endpoint. Efficacy measurement in this study will be assessed as a secondary endpoint, and will be measured by assessing progression-free survival (PFS). PFS will be evaluated based on RECIST v1.1 criteria, 20% progression or any new lesion.

Measurements will be made at baseline and then every 8 weeks during the treatment period until progressive disease is documented, and also at the end of treatment visit if applicable. At baseline, information on all potential sites of tumor lesions should be obtained, at a minimum patients must have a radiologic examination of chest, abdomen and pelvis. Throughout the study period, the same lesions to those identified and measured at baseline must be evaluated using the same technique, the identical contrast agent and the same slice thickness. If additional lesions are suspected, the relevant anatomical regions should be evaluated by appropriate radiologic examinations.

If a patient discontinues treatment prematurely before progression (e.g., due to toxicity), the investigator should perform a complete physical, laboratory and radiological assessment as soon as possible after study drug discontinuation. After treatment discontinuation, tumor assessments should be continued until progression, even if the patient receives other treatments.

For the purposes of defining progressive disease, every effort should be made to obtain radiographical imaging at the defined timepoints.

In cases where radiographic imaging is not possible, clinical progression may be used. Clinical progression is based on the judgment of the investigator.

The complete list of variables to be analyzed for this study will be provided in the statistical analysis plan.

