8.4.2 Progression-free survival

Progression-free survival is defined as the time (days) from start date of study drugs to date of first documented disease progression (radiological or clinical) or death due to any cause, if death occurs before progression is documented. The actual date that the tumor scan was performed will be used for this calculation. Progression-free survival for patients without disease progression or death at the time of the final analysis will be censored at the last date of tumor evaluation. Progression-free survival for patients who have no tumor assessments after baseline will be censored at 1 day. Missing or non-evaluable tumor assessments will not be taken into account in the calculation of PFS. Every effort will be made to obtain radiologic imaging for documentation of progression. In those cases where patients are unable to obtain radiologic examinations due to deterioration of medical condition, the date of clinical progression will be used for the determination of the date of progression. The PFS distribution will be presented descriptively using Kaplan-Meier curves. The median PFS from the Kaplan-Meier distribution will be determined along with the associated 95% confidence interval.

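### Follow-up of patients who stop treatment without progression is contradictory: one set of sections follows them to progression and death, another takes them off study at about 30 days, so PFS events can be lost

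*Combined protocol and SAP*

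**What the plan says.** Two rules stand in the current text for a patient who stops treatment without progression.

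**Follow to the event.**
- Section 7.3: "After treatment discontinuation, tumor assessments should be continued until progression, even if the patient receives other treatments".
- Section 5.2.1: "Regardless of the reason for discontinuation all subjects will be followed for survival until death is documented", with the exception of patients who withdraw consent to follow-up. It adds: "Assessment of survival status will be performed approximately every month". Section 6.8 repeats the survival rule.

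**Stop at about 30 days.**
- Section 7.1.2.5, repeated in Section 2.1, ends participation after the safety follow-up contact, or "after the EOT visit if the Safety Follow-Up Visit is not available), subjects will be off study".
- Section 7.1.2.5 on deaths: "Date and cause of death while on study will be captured".
- Section 7.1.2.4 allows the 30-day contact to be by telephone and lists only concomitant medication and adverse events.
- Table 7 ends with a follow-up column at +1 month, with no scan marked in it.

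Some text falls between the two. Section 5.2.1 says that "available tumor assessments will be recorded in the CRF until PD is documented", which is weaker than the scheduled scans of Section 7.3. Section 7.1.2.5 also asks for four-weekly physician visits until progression, the date of progression, tumour evaluations entered until PD where available, and new cancer therapies. It therefore conflicts with its own off-study sentence.

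Section 8.4.2 defines PFS as time to radiological or clinical progression or death from any cause, with no 30-day limit. Patients without an event at the final analysis "will be censored at the last date of tumor evaluation".

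**The concern.** Site staff cannot follow both rules. Under the off-study rule, a patient who stops for toxicity, patient choice or physician decision has an end-of-treatment scan, a 30-day contact and nothing further. Section 8.4.2 then censors that patient at about the end-of-treatment scan. A later progression or death is not in the data, although other sections say it is to be collected. That overall survival is not an endpoint does not remove the problem, because death is a PFS event.

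PFS is the only efficacy measure named in Section 7.3. Section 1.5 argues that less HFSR will let patients stay on regorafenib longer and so increase efficacy; patients who stop early for toxicity are the group that this argument concerns. If stopping is related to prognosis, censoring them breaks the independence that the Kaplan-Meier estimate needs. Events not collected at the time may be hard to recover later.

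**Working it through.** **1. The plan's own figure.** The documents give no event count or power for PFS. The stated N=34 (Section 8.7) is for any-grade HFSR, 47% against 24%:

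n = [(1.960·√(0.47·0.53) + 0.842·√(0.24·0.76)) / 0.23]² = 33.8, rounded up to 34; power at 34 is 80.2%.

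This reproduces the plan. It contains no PFS quantity, so the contradiction does not touch it.

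**2. Inputs for PFS.**
- From the documents: median PFS 1.9 months (CORRECT) and 3.2 months (CONCUR), Section 1.6; scans every 8 weeks, Section 7.1.2.2; a tumour assessment at the end-of-treatment visit for patients stopping without progression, Section 7.1.2.3, taken here at 14 days after stopping.
- Assumed: a fraction f = 10%, 20% or 30% stop before progression; exponential event times, with the quoted median setting the hazard λ on treatment; after stopping, the hazard is k = 1, 1.5, 2 or 3 times λ; 30% of events are dated exactly (death or clinical progression) and 70% are found at a scan.

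**3. Events lost under the off-study reading.** A scan-detected event is lost if it falls after the end-of-treatment scan, and an exactly dated event if it falls more than 30 days after stopping:

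lost share = f × [0.7·exp(−14kλ) + 0.3·exp(−30kλ)]

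- Highest case (3.2 months, f = 0.30, k = 1): λ = 0.693/97.4 = 0.00712 per day. Lost share = 0.30 × [0.7·0.905 + 0.3·0.808] = 0.263; × 34 = 8.9 events.
- Lowest case (1.9 months, f = 0.10, k = 3): kλ = 3 × 0.693/57.8 = 0.0360 per day. Lost share = 0.10 × [0.7·0.604 + 0.3·0.340] = 0.0525; × 34 = 1.8 events.

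A simulation of the same set-up (400,000 patients per scenario) gives 0.262 and 0.052, and all other scenarios lie between. The range is roughly 2 to 9 of 34.

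**4. Shift in the Kaplan-Meier estimate** (off-study reading minus full follow-up, percentage points, range over both medians and f = 10-30%, from the same simulation):

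| Hazard after stopping | PFS at 16 weeks | PFS at 24 weeks |
|---|---|---|
| 1 × | −0.6 to −3.4 | −0.6 to −2.5 |
| 1.5 × | −0.1 to −0.8 | +0.1 to +0.3 |
| 2 × | +0.2 to +0.7 | +0.5 to +1.8 |
| 3 × | +0.6 to +2.1 | +0.7 to +3.2 |

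At equal hazard the censoring is uninformative. The downward shift there arises because the extra end-of-treatment scan dates some progressions earlier than the 8-week grid would. Overstatement of PFS at both time points appears only when the hazard after stopping is assumed to be two or three times higher.

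The median moves by 0 to about 0.2 months. It is governed by the scan grid: 56 days = 1.84 months and 112 days = 3.68 months, and most simulated medians fall on one of these.

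**5. Comparison with sampling error.** Under the two medians, 16-week PFS is exp(−112λ) = 26.1% and 45.1%. A simple binomial 95% half-width with n = 34 is 1.96·√(0.261·0.739/34) = 14.8 points and 1.96·√(0.451·0.549/34) = 16.7 points.

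**The case against.** The strongest reply is that Section 7.1.2.5 does not simply discard events. It keeps four-weekly visits to progression, asks for the date of progression and for tumour evaluations until PD, accepts telephone follow-up, and anticipates contact with families of patients who have died. To lose a progression, staff would have to disregard these items as well as Sections 5.2.1, 6.8 and 7.3. This stands in part: a careful site could recover many events. But the section records only scans that happen to be available, and its sentence on deaths narrows collection outright.

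A second reply is that off study may mean only the end of adverse-event reporting. That is possible. However, the section already has a separate sentence ending adverse-event reporting after 30 days, and its limit on recording deaths points to the wider meaning.

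A third is that the effect is small and decides nothing. PFS is secondary, descriptive and untested. This stands, and it limits the weight of the point.

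Two stronger readings are tempting. A reader might infer that the censoring is informative and PFS will be overstated. The documents do not show this: they give neither a rate of stopping before progression nor any prognosis after stopping, and the sign of the shift changes with the assumed hazard. A reader might also infer that the median PFS becomes unreliable for this reason. In the scenarios above it hardly moves, and a jump by one scan interval would reflect the grid and not the censoring.

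**Conclusion.** The plan is wrong as written: there is an internal contradiction, in current text, that affects a secondary endpoint. Followed literally, the off-study rule censors patients who stop without progression at about their end-of-treatment scan and loses PFS events that Section 8.4.2 would count. Whether that censoring is informative depends on whether stopping relates to prognosis, which is plausible but not established.

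The loss of roughly 2 to 9 events rests on an assumed 10-30% stopping before progression, the quoted medians, exponential times and no recovery of events after the 30-day contact. The resulting bias, between −3.4 and +3.2 points across the scenarios, is small against the sampling error of 34 patients. The point is worth correcting because the correction is cheap and PFS is the only named efficacy measure, not because any conclusion on HFSR is at risk.

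**What to change.** State one follow-up rule and use it in Sections 2.1, 5.2.1, 6.8, 7.1.2.5, 7.3 and Table 7:

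- Patients who stop without progression remain in follow-up, with the tumour assessments and survival status already specified, until progression or death, unless they withdraw consent to follow-up.
- The 30-day off-study wording in 2.1 and 7.1.2.5 applies to adverse-event collection only.
- The sentence in 7.1.2.5 on deaths is replaced so that deaths after the 30-day contact are recorded and counted in PFS under 8.4.2.
- Table 7 gains a follow-up entry beyond +1 month for these assessments.

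The cost is a wording amendment and a little more data collection after day 30. The scans, four-weekly visits and monthly survival checks are already provided for in 5.2.1, 6.8, 7.1.2.5 and 7.3. The sample size and the primary analysis do not change.

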7.2 Population characteristics

7.2.1 Demographic

Baseline subject data pertaining to demographic information should be documented accordingly in the CRFs include the following:

- Date of Birth (Age)
- Sex
- Race/ethnicity
- Weight
- Height

7.2.2 Medical history

Medical history findings (i.e. previous diagnoses, diseases or surgeries) meeting all criteria listed below will be collected:

- Not pertaining to the study indication
- Start before signing of the informed consent
- Considered relevant to the study.

Detailed instructions on the differentiation between (i) medical history and (ii) adverse events can be found in Section 7.5.1.1.

